4.2.3 Overall survival

The primary analysis of OS in the FAS will be analyzed using stratified log-rank tests using the same methodology as described for the PFS endpoint.

The treatment effect will be estimated by the HR together with its corresponding CI (95% and $[1-adjusted\ alpha] \times 100\%$) from a stratified Cox proportional hazards model.

Kaplan-Meier plots of OS will be presented by treatment group. Summaries of the number and percentage of patients who have died, those still in survival follow-up, those lost to follow-up and those who have withdrawn consent will be provided along with the median OS together with its corresponding 95% CI for each treatment group. The CI for median overall survival will be derived based on Brookmeyer-Crowley method with log-log transformation (SAS Institute Inc. 2018).

The assumption of proportionality will be assessed in the same way as for PFS.

Sensitivity analysis

A sensitivity analysis for OS will examine the censoring patterns to rule out attrition bias with regards to the treatment comparison of primary analysis, achieved by a Kaplan-Meier plot of time to censoring where the censoring indicator of OS is reversed.

The number of patients prematurely censored will be summarized by treatment group. A patient would be defined as prematurely censored if their survival status was not defined at the DCO.

In addition, duration of follow-up will be summarized using medians (as well as minimum and maximum):

- Time from randomization to the date of death (i.e. overall survival) or to the date of censoring (date last known to be alive, for censored patients) summarized in all patients regardless of treatment arm, as well as by treatment arm.
- Time from randomization to the date of censoring in censoring patients only, presented by treatment arm.

Duration of OS follow-up will also be summarized using median (and interquartile range), estimated by analyzing time to censoring with the reverse Kaplan-Meier method (i.e. OS censoring and event flags reversed), presented by treatment arm and overall.

Subgroup analyses and a forest plot will be generated comparing OS between treatments of primary analysis in the same way as previously specified for PFS.

No adjustment to the significance level for testing will be made since all these subgroup analyses will be considered supportive of the primary analysis of OS.

The effect of covariates upon the HR estimate and the consistency of treatment effect between subgroups will be analyzed for OS with regards to the treatment comparison of primary analysis, using the same methods as those described for PFS.

4.2.4 Objective response rate

The ORR will be based on the programmatically derived RECIST 1.1 using BICR assessments for unconfirmed and confirmed responses. The analysis will be performed using a Cochran-Mantel-Haenszel (CMH) test, stratified using the same stratification factors as for the PFS endpoint. The results of the analysis will be presented in terms of the difference in the proportion of patients with a response, together with associated 95% CIs and p-value (2-sided). The confidence intervals for the difference in proportions between treatment groups will be computed using Miettinen and Nurminen's (MN) stratified confidence limits. This analysis will be performed in a subset of the FAS, including all patients with measurable disease at baseline.

A sensitivity analysis will be performed, repeating the analysis of ORR using the site Investigator assessments based on RECIST 1.1, for patients with confirmed and unconfirmed responses.

An exploratory analysis of ORR using the irRECIST 1.1 data obtained from the BICR assessments may be performed where the above analysis will be repeated.

Summaries will be produced that present the number and percentage of patients with a tumor response (CR/PR) based upon the number of patients with measurable disease at baseline per BICR/investigator as appropriate.

For each treatment group, BoR will be summarized by n (%) for each category (CR, PR, SD, PD, and NE). This will be produced for the BICR assessment of RECIST only. No formal statistical analyses are planned for BoR. Analyses will be repeated for patients with confirmed and unconfirmed responses.

Overall visit response data will be listed for all patients in the FAS.

4.2.5 **Duration of response**

Descriptive data will be provided for the DoR in responding patients (i.e. median duration of response and 95% CIs) by treatment group, including the associated Kaplan-Meier curves (without any formal comparison of treatment groups or p-value attached). Analyses will be repeated for patients with confirmed and unconfirmed responses.

4.2.6 Progression-free survival at 18 months and 24 months

The PFS18 and PFS24 (where 1 month equates to 30.4375 days) will be summarized (using the Kaplan-Meier curve) and presented by treatment group. For each treatment group, the PFS18 and PFS24 based on Kaplan-Meier method will be presented, along with their 95% CIs. The computation of the CIs will be based on a log(-log(.)) transformation.

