1.1.2 Secondary objectives

Secondary objectives:	Endpoint/variables:
To assess the efficacy of durvalumab and tremelimumab combination compared to placebo in terms of PFS and OS	PFS using BICR assessments according to RECIST 1.1
To further assess the efficacy of durvalumab monotherapy and durvalumab and tremelimumab combination therapy compared to placebo in terms of ORR, PFS18 ^a , PFS24 ^a , TTDM, OS24, OS36, and PFS2	ORR, PFS18 ^a , PFS24 ^a , and TTDM using BICR assessments according to RECIST 1.1 OS24 and OS36 PFS2
To assess the efficacy of durvalumab and tremelimumab combination therapy compared to durvalumab monotherapy in terms of PFS, OS, and ORR	PFS and ORR using BICR assessments according to RECIST 1.1 OS
To assess disease-related symptoms and HRQoL in patients treated with durvalumab monotherapy and durvalumab and tremelimumab combination therapy compared to placebo using the EORTC QLQ-C30 and QLQ-LC13	EORTC QLQ-C30 and QLQ-LC13: change in symptoms, functioning, and global health status/QoL
To assess the PK of durvalumab monotherapy and durvalumab and tremelimumab combination therapy	Concentration of durvalumab and tremelimumab in serum (such as peak concentration and trough; sparse sampling)
To investigate the immunogenicity of durvalumab monotherapy and durvalumab and tremelimumab combination therapy	Presence of ADA for durvalumab and tremelimumab (confirmatory results: positive or negative)

Secondary objectives:	Endpoint/variables:
To investigate the relationship between PD-L1 expression and spatial distribution within the tumor microenvironment and clinical outcomes with durvalumab monotherapy or durvalumab and tremelimumab combination therapy	PD-L1 expression in tumor and/or immune cells (cutoff ≥ 1%) relative to response/efficacy outcomes (PFS, OS, and ORR). Other PD-L1 cutoffs may also be analyzed

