4.2 Analysis Methods

Results of all statistical analyses will be presented using a 95% confidence interval (CI) and 2-sided p-value, unless otherwise stated.

Table 7 details which endpoints are to be subject to formal statistical analysis, together with pre-planned sensitivity analyses making clear which analysis is regarded as primary for that endpoint. Note, all efficacy endpoints (including PROs) comparing durvalumab monotherapy with placebo will be in all randomized patients (FAS). Efficacy analyses comparing durvalumab and tremelimumab combination therapy with placebo, and durvalumab monotherapy with durvalumab and tremelimumab combination therapy, will be in the combination analysis set, unless otherwise indicated.

Table 7 Pre-planned statistical and sensitivity analyses to be conducted

Endpoints Analyzed Notes	
Progression-free survival	Stratified log-rank tests for:
	 Primary analysis using BICR assessments (RECIST 1.1) for durvalumab monotherapy versus placebo
	 Sensitivity analyses using BICR assessments (RECIST 1.1)
	1) Interval censored analysis – evaluation time bias
	2) Analysis using alternative censoring rules – attrition bias
	 Sensitivity analysis using site Investigator assessments (RECIST 1.1) – ascertainment bias
	 Secondary analysis using BICR assessments (RECIST 1.1) for durvalumab + tremelimumab versus placebo and durvalumab monotherapy versus durvalumab + tremelimumab)
	Subgroup analysis using Cox proportional hazards models
	Additional analysis using Cox proportional hazards models to determine the effect of covariates on the HR estimate
	Additional analysis using Cox proportional hazards models to determine the consistency of treatment effect between subgroups via the approach of Gail and Simon 1985.
Overall survival	Stratified log-rank tests for:
	 Primary analysis (durvalumab monotherapy versus placebo)
	 Secondary analysis (durvalumab + tremelimumab versus placebo and durvalumab monotherapy versus durvalumab + tremelimumab)
	Sensitivity analysis using a Kaplan-Meier plot of time to censoring where the censoring indicator of the primary analysis is reversed – attrition bias
	Subgroup analysis using Cox proportional hazards models
	Additional analysis using Cox proportional hazards models to determine the effect of covariates on the HR estimate
	Additional analysis using Cox proportional hazards models to determine the consistency of treatment effect between subgroups via the approach of Gail and Simon 1985.

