Endpoints Analyzed	Notes
Objective response rate	Cochran-Mantel-Haenszel (CMH) test for difference in proportions using BICR assessments (RECIST 1.1) adjusting for the same factors as the primary endpoint for:
	 Secondary analysis (durvalumab monotherapy and durvalumab + tremelimumab combination therapy versus placebo and durvalumab monotherapy versus durvalumab + tremelimumab)
	Sensitivity analysis using CMH test repeated using the site Investigator assessments (RECIST 1.1)
Duration of response	Kaplan-Meier estimates and confidence intervals
PFS at 18 months and 24 months	Kaplan-Meier estimates and confidence intervals
Time to death or distant metastasis	Stratified log-rank test using BICR assessments (RECIST 1.1)
OS at 24 and 36 months	Kaplan-Meier estimates of survival at 24 months and 36 months and analyses following the method described by Klein et al (Klein et al 2008, Klein et al 2007)
Time from randomization to second progression	Stratified log-rank test using site Investigator assessments
Change from baseline in key symptoms (EORTC QLQ-C30 and QLQ-LC13)	Mixed-model repeated measures analysis
GHS/QoL/Function improvement rate (EORTC QLQ-C30 endpoints)	Logistic regression
Symptom improvement rate (EORTC QLQ-C30 and QLQ-LC13 endpoints)	Logistic regression
Time to GHS/QoL/Function deterioration (EORTC QLQ-C30 endpoints)	Stratified log-rank test
Time to symptom deterioration (EORTC QLQ-C30 and QLQ-LC13 endpoints)	Stratified log-rank test
Treatment-related symptoms (PRO-CTCAE and PGIS)	Presented using summaries and descriptive statistics

BICR Blinded Independent Central Review; CTCAE Common Terminology Criteria for Adverse Event; EORTC European Organisation for Research and Treatment of Cancer; GHS/QoL Global health score/Quality of life; ORR Objective response rate; OS Overall survival; PFS Progression-free survival; PGIS Patient's Global Impression of Severity; PRO Patient-reported outcome; QLQ-C30 30-Item core quality of life questionnaire; QLQ-LC13 Lung cancer module.

[figure not shown]

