4.2.8 Proportion of patients alive at 24 and 36 months

The OS24 and OS36 (where 1 month equates to 30.4375 days) will be summarized (using the Kaplan-Meier curve) and presented by treatment group. For each treatment group, the OS24 and OS36 based on Kaplan-Meier method will be presented, along with their 95% CIs. The computation of the CIs will be based on a log(-log(.)) transformation.

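### PFS18 and PFS24 are secondary comparisons with placebo but have no planned between-arm estimate, and SAP 4.2.8 does not carry through the fixed-time-point analysis that Table 7 lists for OS24 and OS36

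*SAP*

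**What the plan says.** - **Objective.** SAP 1.1.2 (and Protocol Section 3, Table 3) sets out to assess durvalumab and the "combination therapy compared to placebo in terms of ORR, PFS18", and the list goes on to PFS24, TTDM, OS24, OS36 and PFS2.
- **PFS landmarks, text.** SAP 4.2.6: "For each treatment group, the PFS18 and PFS24 based on Kaplan-Meier method will be presented, along with their 95% CIs". Protocol 9.5.1.4 is to the same effect.
- **PFS landmarks, table.** The Table 7 row reads "Kaplan-Meier estimates and confidence intervals".
- **OS landmarks, text.** SAP 4.2.8: "For each treatment group, the OS24 and OS36 based on Kaplan-Meier method will be presented, along with their 95% CIs". Protocol 9.5.1.6 likewise stays within arms.
- **OS landmarks, table.** Table 7 goes further than the text: "Kaplan-Meier estimates of survival at 24 months and 36 months and analyses following the method described" in two cited papers. By their titles in the SAP reference list, one concerns survival curves at a fixed time and the other pseudo-values for censored-data regression. Protocol Table 13 has a matching row.
- **Role of the table.** SAP 4.2 introduces it thus: "Table 7 details which endpoints are to be subject to formal statistical analysis, together with pre-planned sensitivity analyses".
- **Neighbouring endpoints.** The other three endpoints in the same objective each have a between-arm analysis: ORR a Cochran-Mantel-Haenszel test and a difference in proportions with CI (4.2.4), TTDM a stratified log-rank test (4.2.7), PFS2 a stratified log-rank test and hazard ratio (4.2.9).
- **Departures from protocol.** SAP Section 6 does not mention the landmarks.

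**The concern.** The objective asks how each regimen differs from placebo at fixed times. One Kaplan-Meier estimate and CI per arm does not give the size or the precision of that difference. For PFS18 and PFS24 neither text nor table defines a contrast. For OS24 and OS36 a method is cited, but the contrast, scale, stratification and treatment pairs are not stated, so two programmers could produce different outputs, or none.

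The omission does not read as a deliberate choice to stay descriptive. Where the SAP wants no formal comparison it says so, as for duration of response in 4.2.5; 4.2.6 and 4.2.8 carry no such statement.

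At stake is a direct effect estimate with the right precision. If a reader has only the two arms' intervals and compares them by eye, that comparison is stricter than a 95% statement about the difference.

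**Working it through.** The plan states no figure for the landmarks, so this is an illustration at the design effect.

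**Inputs.** About 262 patients in each of the durvalumab and placebo arms; PFS HR 0.65 with placebo median 10 months; OS HR 0.73 with placebo median 24 months; exponential survival (all SAP 1.3).

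**Check of the inputs.** With 1:1 allocation, power = Φ(−ln HR × √d / 2 − z), where d is the number of events.
- PFS: d = 370, two-sided alpha 0.5% gives 0.4308 × 19.235 / 2 − 2.807 = 1.336, power 90.9% (90.3% at the 0.444% level for the primary analysis). The SAP says about 90%.
- OS: d = 348, alpha 3.608% gives 79.9%. The SAP says 80%.

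**Landmark survival.** S_placebo(t) = 0.5^(t/median) and S_durvalumab = S_placebo^HR. For PFS18: 0.5^1.8 = 0.287 and 0.287^0.65 = 0.444. For OS24: 0.500 and 0.500^0.73 = 0.603.

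**Intervals.** SE = √(S(1 − S)/n) with n = 262, assuming no censoring before the landmark. Per-arm CIs use the log(−log) transformation that 4.2.6 and 4.2.8 specify: S^exp(±1.96 × SE / (S × (−ln S))). The difference has SE √(SE_placebo² + SE_durvalumab²) and a normal CI.

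For OS24, SE = 0.0309 (placebo) and 0.0302 (durvalumab). The SE of the difference is 0.0432, so the half-width is 1.96 × 0.0432 = 8.5 points.

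| Landmark | Placebo (95% CI), % | Durvalumab (95% CI), % | Difference (95% CI), points | Separate CIs |
|---|---|---|---|---|
| PFS18 | 28.7 (23.4–34.3) | 44.4 (38.4–50.3) | +15.7 (7.6 to 23.9) | do not overlap |
| PFS24 | 18.9 (14.5–23.9) | 33.9 (28.2–39.7) | +15.0 (7.5 to 22.4) | do not overlap |
| OS24 | 50.0 (43.8–55.9) | 60.3 (54.1–65.9) | +10.3 (1.8 to 18.8) | overlap |
| OS36 | 35.4 (29.6–41.1) | 46.8 (40.7–52.7) | +11.5 (3.1 to 19.8) | overlap narrowly |

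Differences are taken before rounding. The OS24 difference has a nominal p of about 0.017.

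**Range for censoring.** The documents give no effective sample size at the landmarks. With an assumed 210 per arm (about 80% of 262), the difference CIs become 6.6 to 24.8 (PFS18), 6.7 to 23.3 (PFS24), 0.8 to 19.8 (OS24) and 2.1 to 20.8 (OS36). All still exclude zero, and the pattern of overlap is the same.

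**Why the two readings differ.** Non-overlap needs a gap of roughly the sum of the two half-widths; the CI for the difference uses the root of the sum of squares. For PFS18, on symmetric intervals, 5.5 + 6.0 = 11.5 points against 8.1, about 1.4 times as much.

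The combination arm is not illustrated, because the sample-size sections state no assumed effect for it.

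**The case against.** The strongest case for leaving the plan alone has four parts.

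1. **OS24 and OS36 are already covered.** Table 7 lists a fixed-time-point analysis among the formal analyses, and 4.2.8 rules nothing out. This stands to a large extent. A reader might infer that 4.2.8 contradicts Table 7, or that nothing planned answers the OS landmark objective. The documents do not support that: 4.2.8 is silent on an analysis that the table lists. What remains is that the analysis is left undefined.
2. **No conclusion is reversed.** A reader might infer that the plan would present OS24 as showing no difference. That requires ignoring the Table 7 row and applying a CI-overlap rule, and neither document sets such a rule. For PFS18 and PFS24, where the contrast really is missing, the separate intervals already stand apart at the design effect. This stands.
3. **Non-proportional hazards are handled elsewhere.** Protocol 9.5.1.1 mentions landmark analyses as an aid in that situation, but does not speak of landmark differences. SAP 4.2.2 offers piecewise hazard ratios, RMST differences and ratios, a Royston-Parmar model and MaxCombo, all as options, and 4.2.3 carries the proportionality assessment over to OS. So the landmarks are not the only recourse. This stands.
4. **Per-arm reporting follows the definitions.** SAP 3.2.5 and 3.2.7 define the landmarks as Kaplan-Meier estimates, and a reader could approximate an unstratified difference from the two arms. That is true, but the objective is worded as a comparison, and leaving readers to derive the estimate is a poor substitute for reporting it.

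**Conclusion.** The point holds in a limited form. PFS18 and PFS24 are stated comparisons with placebo for which no between-arm estimate is planned anywhere. OS24 and OS36 have a cited method that 4.2.8 does not carry through and that no section specifies.

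The gain from a fix is a direct estimate with correct precision. At the design effect it would be 10 to 16 points, with a half-width of 7.4 to 8.5 points. This rests on exponential survival at the design medians and hazard ratios, 262 per arm, and complete follow-up to the landmark; censoring widens the intervals modestly.

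The landmarks lie outside the multiple testing procedure (SAP 4.2.1) and do not decide whether the study is positive (4.1.1). The stratified log-rank tests and hazard ratios for PFS and OS remain the main comparisons. This is a minor improvement.

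**What to change.** - In SAP 4.2.6 and 4.2.8, add for each landmark the difference in Kaplan-Meier estimates versus placebo with a 95% CI, using the fixed-time-point method that Table 7 already cites for OS24 and OS36. State whether it is stratified.
- Use the FAS for durvalumab versus placebo and the combination analysis set for durvalumab plus tremelimumab versus placebo, as SAP 4.2 does for other efficacy endpoints.
- Label the results nominal and outside the multiple testing procedure.
- Align Table 7 with the text: add the contrast to the PFS18/PFS24 row, and cross-refer the OS24/OS36 row to 4.2.8. Record the change in SAP Section 6.

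If the sponsor prefers to keep the landmarks descriptive, the alternative is to say so in the objective and remove the fixed-time-point entry from Table 7.

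The cost is a few lines of SAP and one extra column per table, with no new data and no alpha.

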4.2.7 Time to death or distant metastasis

TTDM will be analyzed using identical methods as outlined for the analysis of PFS (i.e. a stratified log-rank test) and adjusting for the same set of covariates, but no subgroup analyses will be performed. Medians and Kaplan Meier plots will be presented to support the analysis. The sensitivity analyses outlined in Section 4.2.2 will not be repeated for TTDM. A sensitivity analysis of TTDM may be performed using Investigator assessments according to RECIST 1.1.

4.2.8 Proportion of patients alive at 24 and 36 months

The OS24 and OS36 (where 1 month equates to 30.4375 days) will be summarized (using the Kaplan-Meier curve) and presented by treatment group. For each treatment group, the OS24 and OS36 based on Kaplan-Meier method will be presented, along with their 95% CIs. The computation of the CIs will be based on a log(-log(.)) transformation.

4.2.9 Time from randomization to second progression

PFS2 in the FAS will be analyzed using a stratified log-rank test, using the same methodology as described for the PFS endpoint. The treatment effect will be estimated by the HR together with its corresponding 95% CI from a stratified Cox proportional hazards model. Medians and Kaplan-Meier plots will be presented by treatment group.

The number and percentage of patients experiencing a PFS2 event and the type of progression (Symptomatic progression, Objective radiological progression, Other) will also be summarized by treatment group.

4.2.10 Change in tumor size

The absolute values, change in TL tumor size from baseline and percentage change in TL tumor size from baseline will be summarized using descriptive statistics and presented at each timepoint and by treatment group. The best change in target lesion tumor size from baseline, (where best change in target lesion size is the maximum reduction from baseline or the minimum increase from baseline in the absence of a reduction) will also be summarized and presented by randomized treatment group.

Tumor size will also be presented graphically using waterfall plots for each treatment group, to present each patient's best percentage change in tumor size as a separate bar, with the bars ordered from the largest increase to the largest decrease. Reference lines at the +20% and -30% change in TL tumor size level will be added to the plots, which correspond with the definitions of progression and 'partial' response. All progressions will be marked with a '•'. The scale in these plots will be fixed to be from -100 to 100 to avoid presenting extreme values. Values that are capped as a result of this restriction to the scale are marked with '#'. Values are ordered in descending order with the imputations due to death appearing first followed by a gap followed by all other patients. On each of the waterfall plots the TNM stage (I/II versus III) and receipt of PCI (yes versus no) of each patient will be indicated. Additional waterfall plots showing percentage change in tumor size at specific timepoints may be produced if it is felt that these are warranted to provide greater clarity.

The above outputs will be programmed for the BICR data based upon RECIST assessments.

4.2.11 Patient reported outcomes

4.2.11.1 EORTC QLQ-C30 and **QLQ-LC13**

The PRO endpoints identified as primary are the following 5 lung cancer symptoms:

- Dyspnea: multi-item scale based on 3 questions ("Were you short of breath when you rested; walked; climbed stairs" QLQ-LC13)
- Cough: 1 item ("How much did you cough?" QLQ-LC13)
- Chest pain: 1 item ("Have you had pain in your chest" QLQ-LC13)
- Fatigue: multi-item based on 3 questions ("Did you need rest; Have you felt weak; Were you tired" QLQ-C30)
- Appetite loss: 1 item ("Have you lacked appetite" QLQ-C30)

The physical functioning, role functioning and GHS/QoL domains of the EORTC QLQ-C30 are furthermore pre-specified endpoints of interest.

Mixed-model repeated measures (MMRM) analysis

Change from baseline, using the MMRM analysis, will be examined for dyspnea, cough, and chest pain scores as assessed by the EORTC QLQ-LC13, and GHS/QoL, physical functioning, role functioning, fatigue and appetite loss as assessed by the EORTC QLQ-C30 and as detailed above. The MMRM analysis will examine the change from baseline in the scores for each assessment time point up to PD, death or 24 months. The analysis will be to compare the average treatment effect from the point of randomization until PD, death or 24 months unless there is excessive missing data (defined as missing in >75% of randomized patients in any treatment arm).

It is acknowledged that patients will discontinue treatment at different timepoints during the study and that this is an important time with regards to symptoms and GHS/QoL data collection. To account for this, and to include the discontinuation and follow up visits, a generic visit variable will be derived for each patient in order that the average treatment effect can be analyzed using the above method. Each visit will be assigned a sequential number. The time from randomization to each of these will be derived to select only those visits occurring within the first 24 months of randomization.

As an example, say a patient X attends the first 4 scheduled visits of a weekly schedule and then discontinues treatment, whilst patient Y discontinues treatment after the first scheduled visit, the first 6 generic visits would be as shown in Table 8:

Table 8 Generic visit variable for MMRM analysis

Generic visit	Study day (week)		
	Patient X	Patient Y	
Baseline	Baseline	Baseline	
1	8	7	
2	15	11 (discontinuation)	
3	22	22	
4	29	29	
5	33 (discontinuation)	36	
6	43	43	

The MMRM model will include the fixed, categorical effects of treatment, visit, and treatment-by-visit interaction, TNM stage (I/II versus III) and receipt of PCI (yes versus no) as well as the continuous fixed covariate of baseline score and the baseline score-by-visit interaction. Restricted maximum likelihood (REML) estimation will be used. An overall adjusted mean estimate will be derived that will estimate the average treatment effect over visits giving each visit equal weight. For this overall treatment comparison, adjusted mean estimates per treatment group and corresponding 95% CIs will be presented along with an estimate of the treatment difference, 95% CI and p-value.

An unstructured covariance matrix will be used to model the within-patient error and the Kenward-Roger approximation will be used to estimate the degrees of freedom. If the fit of the unstructured covariance structure fails to converge, the following covariance structures will be tried in order until convergence is reached: toeplitz with heterogeneity, autoregressive with heterogeneity, toeplitz, autoregressive and compound symmetry.

Multiple imputation techniques for missing values may be considered to explore the robustness of any treatment effect.

Time to deterioration

Time to symptom, functioning and GHS/QoL deterioration will be analyzed for each of the symptom scales/items, functional scales, and GHS/QoL in EORTC QLQ-C30 and QLQ-LC13. This will be achieved by comparing between treatment groups using a stratified log-rank test as described for the primary analysis of PFS. The HR and 95% CI for each scale/item will be presented graphically on a forest plot.

For each of the symptom scales/items, functional scales, and GHS/QoL, time to deterioration will be presented using a Kaplan-Meier plot. Summaries of the number and percentage of

patients experiencing a clinically meaningful deterioration or death and the median time to deterioration will also be provided for each treatment group.

Symptom and function and GHS/QoL improvement rate

A summary of the symptom improvement rate for all symptom scales/items in EORTC QLQ-C30 and QLQ-LC13 will be produced. Similarly, a summary of improvement rate for each of the 5 function scales (physical, role, emotional, cognitive, and social) and GHS/QoL will be produced.

Symptom, functional and GHS/QoL improvement rates will be analyzed by comparing between treatment groups using a logistic regression model adjusting for the same factors as the PFS endpoint. The results of the analysis will be presented in terms of an odds ratio together with its associated profile likelihood 95% CI and p-value (based on twice the change in log-likelihood resulting from the addition of a treatment factor to the model). The odds ratio and 95% CI for each scale/item will be presented graphically on a forest plot. If there are very few responses in 1 treatment group, a Fisher's exact test will be considered.

Change from baseline

Summaries of original and change from baseline values of each symptom scale/item, the GHS/QoL score, and each functional domain will be reported by assessment timepoint for each treatment group. Graphical presentations may also be produced as appropriate. Summaries of the number and percentage of patients in each response category at each assessment timepoint for each ordinal item (in terms of the proportion of patients in the categories of improvement, no change, and deterioration as defined in Table 6) will also be produced for each treatment group.

A summary of compliance rate and evaluability rate will be provided for each treatment group, by assessment time point and also for overall. The summary will be provided for the FAS, combination analysis set, and patients who have discontinued treatment.

